#### **D.6. Health Economic Analyses**

**If the intervention is found to be effective, is it cost effective?**

##### D.6.a. Effectiveness Measurement.

A continuous outcome measure, reduction in units of mmHg from baseline to 18 months, will be employed to measure the effectiveness of the intervention (see description of the BP measure in section C.18).

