### D.3. Sample Size and Power Considerations

The sample size estimate is based on the primary hypothesis: veterans randomized to titrated disease management will have lower mean systolic blood pressure at 18 months than veterans randomized to bi-monthly LPN-delivered telephone calls. A 5 mmHg improvement at 18 months will be the definition of a minimally clinically significant difference. This represents the differential between the two treatment groups at 18 month; therefore, the power and sample size considerations, apply even if the control group also improves over the 18 month study period (i.e., "placebo" effect). For example, if the control group improves from 145 mmHg to 142 mmHg, we will have adequate power to detect a 5 mmHg differential improvement – the intervention group improves from 145 to 137 mmHg.

Sample size calculations are based on ANCOVA methods as presented in Borm et al. We used data from previous studies to estimate quantities needed for the sample size calculation. We anticipate a common mean systolic blood pressure of 145 mmHg, a standard deviation of 17.5 mmHg in both treatment groups at baseline, and a correlation between time points equal to 0.4. Finally, based on previous studies, we estimate a 15% attrition rate by 18 months. From the calculation, we determined that **we will need to enroll until we randomize 400 patients (200 randomized in each group)** to detect a 5mmHg difference at 18 months with 80% power and a type-I error of 5%. Based on our prior recruitment experience, we consider this to be feasible given the 18 months timeframe (on average 6-7 patients per week), the potential for over 3,800 eligible individuals in Durham and a total of ~7,900 in all Durham affiliated clinics, and the requested resources. We note that these calculations do not reflect that stratification variables will be included in the final analysis model described above. Stratification variables are expected to account for variability in the outcome. The projected sample size analysis is therefore conservative, and we anticipate that there will be greater power to detect between-group differences with this study size.

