##### D.6.b. Analysis.

The primary objective of the cost-effectiveness analysis will be to estimate the cost per unit difference in effectiveness. The incremental cost effectiveness ratio (ICER) will be calculated as the difference in the average cost per patient between the treatment and control arm divided by the difference in the units of mmHg between the treatment and control arms:

$$ICER = \frac{AVERAGE\ COST_{t=x} - AVERAGE\ COST_{t=0}}{Average\ Reduction\ mmHg_{t=x} - Average\ Reduction\ mmHg_{t=0}}$$

Because we will take an all-cost approach, that is, we assume that any costs unrelated to blood pressure or the intervention will be neutral between the treatment and control group, we will carefully examine the data for outliers. For example, there may be high inpatient costs for patients in the intervention group that are attributable to non-hypertension related comorbidities, necessitating a consideration of this in the analysis. As such, in addition to a consideration of all resource utilization costs described, we will run sensitivity analysis in which we will (1) use diagnostic codes in the inpatient files in order to attribute inpatient utilization to treatment of comorbidities associated with chronic hypertension and/or diabetes, running a sub analysis only on this type of inpatient care; (2) remove patients who are outliers and (3) consider outpatient costs and outpatient HTN-related pharmacy costs exclusively. In addition, we will also perform sensitivity analysis of the ICER calculated on two samples: all patients randomized (complying with the intention to treat principles and a subset of all patients who completed the intervention. Sensitivity analyses will also be performed on types of costs: intervention costs, resource utilization costs, and total costs (intervention costs plus resource utilization costs). If there are no differences in resource utilization across arms, we will simply include the intervention

costs in the ICER calculation. All dollars will be expressed in 2011 dollars, using the Consumer Price Index for Medical Care for medical items or Consumer Price Index for other items.

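### The ICER denominator is not tied to the primary model's month-18 contrast; read as raw mean changes, its standard error is about 20% larger at the plan's own correlation

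*Protocol*

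**What the plan says.** D.6.a defines effectiveness for the economic analysis: "A continuous outcome measure, reduction in units of mmHg from baseline to 18 months, will be employed to measure the effectiveness of the intervention". Its only cross-reference is to C.18, which describes how blood pressure is measured. D.6.b takes the difference in average cost per patient "divided by the difference in the units of mmHg between the treatment and control arms", and the displayed formula shows the denominator as one average reduction in mmHg minus another. No estimator is named.

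D.2 estimates the month-18 effect on the same outcome with a repeated-measures model in PROC MIXED and tests the arm contrast at month 18. Equation (1) has time and arm-by-time terms but no arm main effect, so the arms share one baseline mean. D.5 refers the continuous adherence analysis back to that model by name; D.6 makes no such link.

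D.3 sizes the trial by ANCOVA with "a standard deviation of 17.5 mmHg in both treatment groups at baseline", "a correlation between time points equal to 0.4", and "we estimate a 15% attrition rate by 18 months".

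On samples, D.6.b names all randomized patients and, separately, those who completed the intervention, both under sensitivity analysis. D.8 applies intention to treat to all analyses. D.7 relies on the likelihood model under missing at random and says that multiple imputation will be explored. D.6.b bootstraps a confidence interval for the base-case ratio only if the SBP difference is significant.

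**The concern.** The protocol describes one quantity, the arm difference in SBP at 18 months, in two ways. The primary analysis estimates it with a model that uses baseline efficiently. The economic analysis writes it as a difference of average reductions. If those averages are taken as raw arm means, the baseline value is subtracted in full although its correlation with month 18 is only 0.4, and this adds noise.

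Two things follow. First, the report could show two SBP effects, with H3 resting on the less precise one. The significance condition in D.6.b would naturally be judged on the primary result, so the ratio could be computed after the model has passed while the raw denominator is still compatible with zero. Second, a raw reduction does not exist for a patient without a month-18 reading unless one is imputed. D.3 expects 15% attrition by then, and D.6 does not say how such patients enter the ratio.

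**Working it through.** **Inputs, all from D.3:** SD σ = 17.5 mmHg (stated at baseline, taken as common to both time points), correlation ρ = 0.4, difference 5 mmHg, 200 randomized per arm, 15% attrition, hence 200 × 0.85 = 170 evaluable per arm. Type I error is 5%; a two-sided test is assumed, since sidedness is not stated.

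**1. The plan's own figure.** D.3 claims a "5mmHg difference at 18 months with 80% power" with 400 randomized.
- Unadjusted n per arm: 2 × [17.5 × (1.960 + 0.842) / 5]² = 192.3.
- ANCOVA: 192.3 × (1 − 0.4²) = 161.5, so 162 evaluable.
- Attrition: 162 / 0.85 = 190.6, so 191 per arm and 382 in total.

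The 400 is a little above this minimum. With 170 evaluable per arm, ANCOVA power is 82.0%, so the stated 80% is reproduced and the sizing assumes a baseline-adjusted estimate.

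**2. Variance per patient under each estimator.**
- Raw change: 2σ²(1 − ρ) = 2 × 306.25 × 0.6 = 367.5.
- Month-18 value alone: σ² = 306.25.
- Baseline-adjusted: σ²(1 − ρ²) = 306.25 × 0.84 = 257.25.

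**3. Standard error of the arm difference**, √(variance × 2/170), **and power for 5 mmHg.**

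| Estimator | SE (mmHg) | Power |
|---|---|---|
| Raw change | 2.079 | 67.2% |
| Month 18 alone | 1.898 | 75.0% |
| Baseline-adjusted | 1.740 | 82.0% |

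Raw change against baseline-adjusted: variance ratio 367.5 / 257.25 = 1.43; SE ratio √[2/(1 + ρ)] = √(2/1.4) = 1.195. At ρ = 0.4, subtracting baseline is less precise than ignoring it.

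**4. Check against a longitudinal model.** Take 200 per arm, a common baseline mean, compound symmetry with ρ = 0.4, and monotone dropout of 5% at each of months 6, 12 and 18 (covariance and dropout pattern assumed). The month-18 contrast has SE 1.730, and 2.079 / 1.730 = 1.20.

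**5. Sensitivity.**
- Correlation: the SE ratio is 1.24 at ρ = 0.3, 1.15 at 0.5, 1.12 at 0.6 and 1.08 at 0.7.
- Truncated baseline: enrolment cut-offs may narrow the baseline SD to s₀ while the regression slope (0.4) and residual variance (257.25) stay as they are. The variance ratio is then 1 + 0.6² × s₀² / 257.25. For s₀ = 10 it is 1.14 (SE +7%); for s₀ = 12 it is 1.20 (SE +10%). The values 10 and 12 are assumptions.

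**6. How far the two estimates can part.** With complete month-18 data, their difference has SD √(2.079² − 1.740²) = 1.14 mmHg and their correlation is 1.740 / 2.079 = 0.84. Simulating pairs on this basis with a true effect of 5 mmHg, the adjusted estimate is significant and the raw change is not in about 17% of trials. This describes the denominator only. The protocol gives no cost variance, so the effect on the ICER interval cannot be computed.

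**7. Do the two target the same quantity?** In equation (1) the model-based reduction is −β₃ in the control arm and −(β₃ + β₆) in the intervention arm. The difference is −β₆, so the month-18 contrast has exactly the meaning that D.6 requires.

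**The case against.** The best defence is that D.6 names a quantity and no estimator. The protocol also uses change wording for the primary outcome in C.18 and for H1, and both are analysed by the mixed model. As step 7 shows, that model yields the very difference D.6.b asks for, so the text is compatible with the model-based estimate. Naming the estimator could also be left to a later analysis plan. It stands that raw means are an inference. But the protocol writes out the ratio, cross-refers only to the measurement section, and omits the link to the model that D.5 makes. The natural reading is the inefficient one.

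A reader might go further and infer that the ratio uses completers only, or that cost and effect come from different samples. The documents do not support this. D.6.b names all randomized patients, D.8 applies intention to treat throughout, and D.7 leaves multiple imputation open. What remains is that the handling of a missing month-18 SBP in the ratio, and the sample behind the base case, are not stated.

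Nor is bias shown. With complete data and randomization both estimators target the same difference; bias could come only through missing month-18 readings. It is also fair that D.6 tests nothing on the denominator, so the power and discordance figures illustrate its imprecision and do not measure damage to the ICER interval. D.2 further leaves the form of time and the covariance open, so the comparator is approximate.

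**Conclusion.** The point holds as one of precision and consistency in a secondary analysis. D.6 defines the denominator without tying it to the D.2 month-18 contrast. Read as raw mean changes, its standard error is about 20% larger than the baseline-adjusted one (2.08 against 1.74 mmHg), given D.3's SD of 17.5, correlation of 0.4 and 170 evaluable per arm, and about 7–10% larger if the baseline SD is really 10–12. The primary result and the trial's sizing are untouched. The consequence for the ICER interval has not been quantified. The plan should be changed, because the better estimator is already in the protocol and answers the same question.

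**What to change.** In D.6.a and D.6.b, define the ICER denominator as the month-18 arm difference from the D.2 mixed model, fitted to all randomized patients under intention to treat, and name that as the base case. State that each bootstrap replicate resamples patients and refits the model together with the cost difference. Patients without a month-18 SBP then contribute through their observed visits under the missing-at-random assumption of D.7, and the ratio uses the same SBP effect as the primary analysis. The completer ICER can stay as a sensitivity analysis. The cost is a few sentences and 1,000 model refits; no new data are needed.

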##### D.6.b. Analysis.

The primary objective of the cost-effectiveness analysis will be to estimate the cost per unit difference in effectiveness. The incremental cost effectiveness ratio (ICER) will be calculated as the difference in the average cost per patient between the treatment and control arm divided by the difference in the units of mmHg between the treatment and control arms:

$$ICER = \frac{AVERAGE\ COST_{t=x} - AVERAGE\ COST_{t=0}}{Average\ Reduction\ mmHg_{t=x} - Average\ Reduction\ mmHg_{t=0}}$$

Because we will take an all-cost approach, that is, we assume that any costs unrelated to blood pressure or the intervention will be neutral between the treatment and control group, we will carefully examine the data for outliers. For example, there may be high inpatient costs for patients in the intervention group that are attributable to non-hypertension related comorbidities, necessitating a consideration of this in the analysis. As such, in addition to a consideration of all resource utilization costs described, we will run sensitivity analysis in which we will (1) use diagnostic codes in the inpatient files in order to attribute inpatient utilization to treatment of comorbidities associated with chronic hypertension and/or diabetes, running a sub analysis only on this type of inpatient care; (2) remove patients who are outliers and (3) consider outpatient costs and outpatient HTN-related pharmacy costs exclusively. In addition, we will also perform sensitivity analysis of the ICER calculated on two samples: all patients randomized (complying with the intention to treat principles and a subset of all patients who completed the intervention. Sensitivity analyses will also be performed on types of costs: intervention costs, resource utilization costs, and total costs (intervention costs plus resource utilization costs). If there are no differences in resource utilization across arms, we will simply include the intervention

costs in the ICER calculation. All dollars will be expressed in 2011 dollars, using the Consumer Price Index for Medical Care for medical items or Consumer Price Index for other items.

We will use stochastic methods to evaluate variability associated with the cost-effectiveness ratio. If the difference in SBP is significantly higher in an intervention arm relative to the standard care arm, the 95% confidence interval for the base-case cost-effectiveness ratio will be computed with nonparametric bootstrapping using the bias-corrected percentile method (1,000 repetitions). The bootstrapping procedure will allow us to use limited information to estimate the sampling distribution of mean costs per patient, which then will allow us to make inference about the true population sampling distribution of mean costs without making strong distributional assumptions. Using bootstrapped confidence intervals will help us bind our estimates in a way that reduces the influence of outliers. This procedure is relevant for thinking about implementation effects of the intervention, when there will be much larger sample sizes and a ICER not limited by small sample properties.

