### **C. 13. Intervention Component – Pharmacist-Directed Algorithmic Medication Management [high/level 2 resource intensity]**

Many patients require medication intensification to achieve targets for BP. Appropriate medication management requires accurate and timely information on the patient's current level of disease control, treatment adherence, evidence-based recommendations, and potential barriers to successful implementation. Patients who meet criteria for high/level 2 resource intensity disease management will receive medication management from a clinical pharmacist, who will be backed up by an MD ([name] or his appropriately licensed back-up/replacement who could be a mid-level provider). Pharmacists are authorized to make medication changes according to accepted treatment algorithms and based on their scope of practice. Via CPRS, the pharmacist will also communicate these changes to the patient's PCP. While pharmacists may collaborate with the patients' providers when clinically indicated, they do not have to rely on providers to make the changes. The goal of the medication component of the intervention is not to replace clinic based management, but rather to supplement it based on home BP readings in order to more efficiently implement interventions that may otherwise be left until the next provider appointment. The pharmacist will attempt to contact patients every month while they are in the high-intensity titration level of the intervention. At the pharmacist's discretion, patients may be asked to come to the Durham VAMC for an in-person meeting, however, most interactions will be conducted over the phone. During each encounter, the pharmacist will have information from both CPRS and the behavioral-telephone calls conducted as part of the intervention so information on such topics as patient medication and barriers to adherence can be available. During the initial encounter the pharmacist will assess the patient's medication adherence, review all BP related medications, discuss the purpose of each medication, and the appropriate administration of each medication. While not explicitly planned, the pharmacist (or appropriately licensed clinical backup) may discuss other medicines if he or she feels that this is needed to appropriately manage BP medication. At subsequent contacts the pharmacist will review any medication changes with the patients and update patients' medication lists. All calls will be indicated with a note in the Durham VAMC electronic health record.

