### **C.20.b. Intervention Cost Measurement**

We will assess intervention-related costs and resource-utilization costs to create a complete picture of the costs that would be incurred if the intervention were adopted system-wide. We will examine outcomes over 18 months, matching the timing of the measurement of the primary outcome. Intervention costs include labor and capital costs. Labor will include interventionist time, assessed using VA Human Resources data for salaries and carefully tracked study data on time spent per task. LPN, RN and PharmD time on calls, clinic time devoted to the study, and training costs to implement the study will all be included at the relevant wage and fringe benefit rates. We do not anticipate that the interventions will place additional time burden on physicians. We will assume that capital costs such as overhead costs, office space and supply costs, and telephone services costs will be neutral because implementation would use existing capitol. In addition, equipment costs of the electronic home BP monitoring units (and batteries) will be included, using current market prices.

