### **C.20.c. Patient Cost and Utilization.**

All resource utilization and cost data will come from Decision Support System (DSS) data (or equivalent database if the VA data storage locations change before the end of the study), including the DSS Outpatient (OPAT) National Data Extract (NDE), the DSS NDE SAS Pharmacy Dataset, and the DSS Inpatient Discharge Extract File (DISCH). We will measure VA outpatient and inpatient utilization and costs by treatment or control over 18 months. Outpatient encounters will be categorized using clinic stop codes into primary care visits, specialty care visits, and other outpatient care (laboratory, radiology, surgery, nursing, and all other clinical visit and ancillary services and encounters not already mentioned), as well as a count of total encounters (unique CLSTOPS) and total costs (OCST\_TOT). We will also examine hypertension-related outpatient pharmacy prescription counts and costs using an identification method developed in the HINTS study (SAS algorithm of HTN-related outpatient drugs developed by [name], Puget Sound VA), in order to compare them to total outpatient pharmacy costs (DISP\_COST plus ACT\_Cost). The utilization most likely to be affected by the intervention will be outpatient and pharmacy-related. For comparability with other studies, however, we will also examine inpatient utilization and costs. Inpatient encounters will include whether there was any inpatient care in the study period, total days in the hospital (DISDAY minus ADMITDAY, DAYS), and total inpatient costs (DCST\_TOT). We will also use diagnostic codes to categorize inpatient stays that are hypertension related. The analysis will focus on differences in utilization and costs in the study period but we also will examine costs in the 18 months pre-intervention to check for temporal trends. Specific variables outlined above represent applicable variables as of the time of the initial protocol submission. Because of changing VA data structures, the precise variable names may change over the course of the study. In addition we will evaluate costs from the perspective of both patient and society.

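### Total cost adds logged pharmacist time to all VA encounter costs with no step to remove study contacts: any pharmacist contact recorded as a costed encounter would be charged twice, in the intervention arm only

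*Protocol*

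**What the plan says.** Two cost streams are defined and then added.

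- **Intervention cost (C.20.b).** "Labor will include interventionist time, assessed using VA Human Resources data for salaries and carefully tracked study data on time spent per task". On content: "LPN, RN and PharmD time on calls, clinic time devoted to the study, and training costs to implement the study will all be included". C.15 confirms that the intervention software records the number and duration of calls for use in the cost analyses.
- **Utilization cost (C.20.c).** "All resource utilization and cost data will come from Decision Support System (DSS) data". Outpatient encounters are sorted by clinic stop code into primary care, specialty care and a residual class that takes in everything else. Total encounters and total outpatient cost are also taken. No exception is made for contacts that the study itself delivers.
- **The sum (D.6.b).** Sensitivity analyses by type of cost cover each stream alone and "total costs (intervention costs plus resource utilization costs". The same section declares an all-cost approach. It falls back to intervention costs alone only if utilization does not differ between the arms.

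On level 2 (pharmacist) care, C.13 says "All calls will be indicated with a note in the Durham VAMC electronic health record" and that "patients may be asked to come to the Durham VAMC for an in-person meeting", at the pharmacist's discretion. C.16 gives control patients LPN calls only. Table 2 expects about 70 of the 200 intervention patients at level 2 at baseline.

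**The concern.** The utilization stream is written to be exhaustive, and the intervention stream prices contacts that clinical staff deliver inside the same VA system. A pharmacist contact that is timed in the study log and also carries a costed DSS encounter appears in both streams, and the plain sum counts it twice.

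Such an error would not cancel between arms. Study pharmacist contacts exist only in the intervention arm, so the duplicate would push the incremental cost, and with it the ICER that serves hypothesis H3 (A.1.c), in one direction.

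It could also act earlier in the analysis. D.6.b lets an observed difference in utilization decide whether utilization costs enter the ICER. Encounters generated by the study could produce that difference themselves, and so bring in the cost stream that contains the duplicate.

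**Working it through.** The protocol gives no cost figure to reproduce. The check is a comparison of the text, followed by an illustration of size.

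**Text comparison**

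1. Is pharmacist time in the intervention stream? Yes: call time and clinic time, from tracked data (C.20.b, C.15).
2. Would a costed pharmacist encounter be in the utilization stream? Yes: the stream is all DSS outpatient cost, with a residual class (C.20.c).
3. Is there a rule separating the two? None in C.20.b, C.20.c or D.6.
4. Do pharmacist contacts leave a trace in the VA record? Every call gets a note (C.10.a.3, C.13), and some contacts may be in person at the VAMC (C.13).
5. Does that trace become a costed DSS encounter? The protocol does not say. The finding depends on this step.
6. Do the planned sensitivity analyses in D.6.b remove the overlap? The first restricts inpatient care by diagnosis, the second drops outlying patients, and the third keeps outpatient costs. None removes study contacts. Only the version with intervention costs alone is free of the problem.

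**Illustration of size**

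Inputs from the protocol:
- share at level 2 at baseline: 70/200 = 0.35 (Table 2)
- one pharmacist contact per month while at level 2 (C.13)
- effect of 5 mmHg, the minimally clinically significant difference (D.3)

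Assumptions, not in the protocol:
- every monthly call becomes a costed DSS encounter
- DSS cost of $20 to $100 per contact
- the 35% share stays constant for the period shown

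Formulas:
- contacts per intervention patient = 0.35 × months at level 2
- duplicated cost = contacts × DSS cost per contact
- shift in the ICER = duplicated cost / 5 mmHg

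| Months at level 2 | Contacts per intervention patient | Duplicated cost per intervention patient | Shift in ICER per mmHg |
|---|---|---|---|
| 6 | 0.35 × 6 = 2.1 | $42 to $210 | $8.40 to $42 |
| 12 | 0.35 × 12 = 4.2 | $84 to $420 | $16.80 to $84 |
| 18 | 0.35 × 18 = 6.3 | $126 to $630 | $25.20 to $126 |

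If no call becomes a costed encounter, every entry is $0 as far as calls are concerned. In-person meetings are not in the table, because the protocol gives no expected number.

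For scale, Table 1 reports about $112 per patient per year for one earlier programme and about $460 for another. Over 18 months that is 1.5 × 112 = $168 and 1.5 × 460 = $690. On this common time base the low end of the illustration is small and the high end is of the same order as a whole programme.

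**The case against.** The strongest objection is that the double charge rests on a fact the protocol does not state. A note in the health record is not the same as a stop-coded, costed encounter. A reader might infer from the notes and the VAMC meetings that double charging is built into the plan. The text does not support that: it leaves the possibility open for calls and meetings alike. This part of the objection stands, and the point is worded as conditional for that reason.

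A reader might also infer that intervention contacts in general are affected. The protocol ties routine record notes to pharmacist contacts. It states none for RN or LPN calls, and about 130 of the 200 intervention patients start at the RN level. In-person meetings are discretionary, most contact is by telephone, and no sentence says that the clinic time in C.20.b means those meetings. The exposure shown by the text is at level 2.

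On size, it is tempting to price the duplicate at a pharmacist's wage. The duplicate would carry the DSS encounter cost, which is not given. Nor is 18 months at level 2 for all 70 patients the expected course: titration at 6 and 12 months can move patients down (C.9.b). It can also move others up, so the baseline share is neither a firm ceiling nor a forecast.

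Two further arguments carry less weight. The sum quoted above stands in a list of sensitivity analyses, and intervention costs are also to be reported alone, which would help a reader see where a difference arises. But the all-cost approach and the fallback rule make the same sum the default for the main ICER. It can also be said that de-duplication belongs in an analysis plan. A separate plan could settle it. However, the protocol itself fixes the cost sources down to variable names and fixes the sum, and an analysis that followed it literally would carry any overlap forward.

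**Conclusion.** The point holds as a conditional risk at the pharmacist level. As written, D.6.b adds logged staff and clinic time to an all-inclusive DSS total with no separation. Where a study pharmacist contact is recorded as a costed DSS encounter, it is counted twice, in the intervention arm only. Incremental cost and the ICER are then biased upward, and the rule on including utilization costs can be triggered by the study's own contacts.

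The size cannot be fixed from the protocol. It ranges from zero to amounts comparable with the cost of earlier programmes, depending on whether contacts are booked, what DSS charges for them and how long patients stay at level 2. The primary blood pressure analysis is not touched. Only the secondary cost-effectiveness analysis is, and that is planned only if the intervention proves effective. The change should be made because it is cheap and does no harm if there turns out to be no overlap. Confidence is medium, because the step from record note or meeting to costed encounter is unknown.

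**What to change.** In C.20.c and D.6.b, add a rule along these lines:

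- Identify study-delivered encounters by matching the intervention log (date and clinician) to the DSS outpatient records, in both arms.
- Remove the matched encounters from DSS encounter counts and costs before utilization is compared between arms and before the two cost streams are summed.
- Count those contacts once, through the logged intervention cost.
- Keep laboratory tests and prescriptions in the DSS totals, since the log of staff time does not price them.

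C.15 speaks mainly of calls, so the text should also say that in-person pharmacist meetings are logged with date and clinician.

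The cost is a small record-matching step between two sources already planned. If study contacts prove not to generate costed encounters, the match finds nothing and the results do not change.
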